4.2.2.2.3 Secondary Endpoint of ORR based on BICR

Summaries will also be produced for ORR assessed by BICR using the TPAS, SAF and CAS.

In detail, for SAF:

- savolitinib (300 mg od, 300 mg bid and 600 mg od, respectively) in combination with osimertinib in patients with EGFRm+, MET amplified/overexpressed (FISH10+ and/or IHC90+), locally advanced or metastatic NSCLC who have progressed following osimertinib
- savolitinib (300 mg od, 300 mg bid and 600 mg od, respectively) in combination with osimertinib in patients with EGFRm+, MET amplified/overexpressed (FISH5+ and/or IHC50+), locally advanced or metastatic NSCLC who have progressed following osimertinib.

Finally, summaries will be produced using the CAS for:

- 300 mg bid (savolitinib) + osimertinib
- 300 mg bid (savolitinib) + placebo.

4.2.2.3 Secondary Endpoint – Duration of Response

4.2.2.3.1 Target Population Analysis Set

Duration of response and time to onset of objective response will be summarised for patients who achieved objective response during the study using the TPAS. Median duration of response, and quartiles will be summarised, including 95% CI. The percentage of patients still in response at 3, 6, 9 and 12 months, along with the 95% CI will be presented. Onset of response relative to subsequent therapy will also be summarised.

Kaplan-Meier plots of DoR in the responding patients and Swimmer plots showing the profile of each patient who responds will also be produced based on the TPAS.

4.2.2.3.2 Safety Analysis Set

The summaries described in the above section 4.2.2.3.1 will be produced using the SAF for:

- savolitinib (300 mg od and 600 mg od, respectively) in combination with osimertinib in patients with EGFRm+, MET amplified/overexpressed (FISH10+ and/or IHC90+), locally advanced or metastatic NSCLC who have progressed following treatment with 1L osimertinib

savolitinib (300 mg od, 300 mg bid and 600 mg od, respectively) in combination with osimertinib in patients with EGFRm+, MET amplified/overexpressed (FISH5+ and/or IHC50+), locally advanced or metastatic NSCLC who have progressed following osimertinib

4.2.2.3.3 Contribution of Components Analysis Set

The analyses described in the above section 4.2.2.3.1 will be produced using the CAS for:

- 300 mg bid (savolitinib) + osimertinib

- 300 mg bid (savolitinib) + placebo.

4.2.2.3.4 Secondary endpoint of DoR based on BICR

Summaries will also be produced for DoR assessed by BICR using the TPAS, SAF and CAS. In details for SAF:

- savolitinib (300 mg od, 300 mg bid and 600 mg od, respectively) in combination with osimertinib in patients with EGFRm+, MET amplified/overexpressed (FISH10+ and/or IHC90+), locally advanced or metastatic NSCLC who have progressed following osimertinib
- savolitinib (300 mg od, 300 mg bid and 600 mg od, respectively) in combination with osimertinib in patients with EGFRm+, MET amplified/overexpressed (FISH5+ and/or IHC50+), locally advanced or metastatic NSCLC who have progressed following osimertinib.

Finally, summaries will be produced using the CAS for:

- 300 mg bid (savolitinib) + osimertinib
- 300 mg bid (savolitinib) + placebo.

4.2.2.4 Secondary Endpoint – Progression Free Survival

4.2.2.4.1 Target Population Analysis Set

PFS will be summarised using the Kaplan-Meier methodology and will be based on TPAS. Median time to progression, and quartiles will be summarised, including 95% CI. The percentage of patients being progression-free at 3, 6, 9, 12, 18, 24, 30 and 36 months, along with the 95% CI, and the median and range of duration of follow-up in censored patients, will also be presented. Kaplan Meier curves will also be plotted.

Treatment status at time of progression will be presented, showing patients who were on savolitinib and/or osimertinib at time of progression and patients who discontinued treatment prior to progression. Treatment status after progression will also be summarised, showing the patients who continued to receive savolitinib and/or osimertinib after progression.

4.2.2.4.1.1 Subgroup analyses

Subgroups analyses of PFS will be conducted on the same subgroups as for ORR and based on TPAS. Refer to section 4.2.2.1.1 for details on the specific subgroups and Appendix “A”.

4.2.2.4.2 Safety Analysis Set

The summaries described in the above section 4.2.2.4.1 will be produced using the SAF for:

- savolitinib (300 mg od and 600 mg od, respectively) in combination with osimertinib in patients with EGFRm+, MET amplified/overexpressed (FISH10+ and/or IHC90+), locally advanced or

metastatic NSCLC who have progressed following treatment with 1L osimertinib

- savolitinib (300 mg od, 300 mg bid and 600 mg od, respectively) in combination with osimertinib in patients with EGFRm+, MET amplified/overexpressed (FISH5+ and/or IHC50+), locally advanced or metastatic NSCLC who have progressed following osimertinib.

4.2.2.4.2.1 Subgroup analyses

Subgroups analyses of PFS in SAF patients treated with savolitinib 300 mg od in combination with osimertinib with EGFRm+, MET amplified/overexpressed, will be conducted on the same subgroups as for ORR. Refer to section 4.2.2.2.2.1 for details on the specific subgroups and Appendix “A”.

4.2.2.4.3 Contribution of Components Analysis Set

PFS will be summarised using the Kaplan-Meier methodology and will be based on CAS for:

- 300 mg bid (savolitinib) + osimertinib
- 300 mg bid (savolitinib) + placebo.

Median time to progression, and quartiles will be summarised, including 95% CI. The percentage of patients being progression-free at 3, 6, 9, 12, 18, 24, 30 and 36 months, along with the 95% CI, and the median and range of duration of follow-up in censored patients, will also be presented. Kaplan Meier curves will also be plotted.

PFS will be analysed using a stratified log-rank test adjusting for the stratification used in randomisation for the generation of the p-value. The effect of treatment will be estimated by the HR together with its corresponding 95% CI for the CAS. An HR less than 1 will favour savolitinib plus osimertinib. The HR and its CI will be estimated from a Cox Proportional Hazards model (with ties = Efron and baseline stratification) and the CI calculated using a profile likelihood approach. If there are insufficient events per strata, a log-rank test will be used to analyse PFS instead of a stratified log-rank test.

Treatment status at time of progression will be presented, showing patients who were on savolitinib and/or osimertinib at time of progression and patients who discontinued treatment prior to progression.

4.2.2.4.4 Secondary endpoint of PFS based on BICR

Summaries will also be produced for PFS assessed by BICR using the TPAS and SAF.

In details for SAF:

- savolitinib (300 mg od, 300 mg bid and 600 mg od, respectively) in combination with osimertinib in patients with EGFRm+, MET amplified/overexpressed (FISH10+ and/or IHC90+), locally advanced or metastatic NSCLC who have progressed following osimertinib
- savolitinib (300 mg od, 300 mg bid and 600 mg od, respectively) in combination with osimertinib in patients with EGFRm+, MET amplified/overexpressed (FISH5+ and/or IHC50+),

locally advanced or metastatic NSCLC who have progressed following osimertinib.

4.2.2.5 Secondary Endpoint – Overall Survival

4.2.2.5.1 Target Population Analysis Set

OS will be summarised for TPAS set using the Kaplan-Meier methodology. Median time to event, and quartiles will be summarised, including 95% CI for overall survival (months). Survival rate at 12, 15, 18, 24, 30 and 36 months with 95% CI, and the median and range of duration of follow-up in censored patients, will be included. Kaplan-Meier curves will also be plotted.

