To describe the difference in the efficacy of savolitinib (300 mg bid) in combination with osimertinib and savolitinib (300 mg bid) in combination with placebo in patients with EGFRm+, MET amplified/overexpressed (FISH10+ and/or IHC90+) ^a , locally advanced or metastatic NSCLC who have progressed following treatment with 1L osimertinib therapy under CSP version 7.0.	
• ORR by investigator assessment in accordance with RECIST 1.1

To determine the efficacy of savolitinib (300 mg od and 600 mg od, respectively) in combination with osimertinib in patients with EGFRm+, MET-amplified/overexpressed (FISH10+ and/or IHC90+)^a, locally advanced or metastatic NSCLC who have progressed following treatment with 1L osimertinib.
	
 • ORR, DoR, and PFS, by investigator assessment in accordance with RECIST 1.1. • OS

To determine the efficacy of savolitinib (300 mg od, 300 mg bid, and 600 mg od, respectively) in combination with osimertinib in patients with EGFRm+, MET-amplified/overexpressed (FISH10+ and/or IHC90+)^a, locally advanced or metastatic NSCLC who have progressed following treatment of ≥ 2L osimertinib.
	
 • ORR, DoR, and PFS, by investigator assessment in accordance with RECIST 1.1. • OS

To determine the efficacy of savolitinib (300 mg od, 300 mg bid, and 600 mg od, respectively) in combination with osimertinib in patients with EGFRm+, MET-amplified/overexpressed (FISH5+ and/or IHC50+)^b, locally advanced or metastatic NSCLC who have progressed following osimertinib.
	
 • ORR (except 300 mg od), DoR, and PFS by investigator assessment in accordance with RECIST 1.1. • OS

To determine the efficacy of (1) 300 mg od, 300 mg bid and 600 mg od of savolitinib in combination with osimertinib in patients with EGFRm+ MET amplified/overexpressed (FISH 10+ and/or IHC90+)^{a,b}; (2) 300 mg od, 300 mg bid and 600 mg od of savolitinib in combination with osimertinib in patients with EGFRm+ MET amplified/overexpressed (FISH5+ and/or IHC50+)^b (3) savolitinib 300 mg bid in combination with osimertinib and savolitinib 300 mg bid in combination with placebo, respectively, in patients with EGFRm+ MET amplified/overexpressed (FISH10+ and/or IHC90+)^a following treatment with 1L osimertinib.
	
 • ORR, DoR, and PFS assessed by BICR in accordance with RECIST 1.1

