9.4.3.2 Analysis of the secondary endpoints

Analyses for the efficacy secondary endpoints will be summarised using the TPAS, CAS, and SAF datasets (see Section 9.3 for analysis set definitions).

Objective response rate

To describe the difference in the efficacy of savolitinib (300 mg bid) in combination with osimertinib and savolitinib (300 mg bid) in combination with placebo in patients with EGFRm+, MET amplified/overexpressed (FISH10+ and/or IHC90+), locally advanced or metastatic NSCLC who have progressed following treatment with 1L osimertinib therapy under CSP version 7.0, ORR with 95% confidence intervals will be constructed in the CAS for:

- Osimertinib + savolitinib (300 mg bid)
- Placebo to osimertinib + savolitinib (300 mg bid)

Additional details for the analysis of ORR on other dosing regimen/lines of therapy/biomarker population will be specified in the SAP.

Duration of response

The DoR will be defined as the time from the date of first documented response until date of documented progression or death in the absence of disease progression (ie, date of PFS event or censoring—date of first response+1). The end of response should coincide with the date of progression or death from any cause used for the PFS endpoint. The time of the initial response will be defined as the latest of the dates contributing towards the first visit response of CR or PR.

If a patient does not progress following a response, then their DoR will use the respective PFS censoring time.

If there are sufficient numbers of responders, and sufficient numbers of responses that have progressed by the point of the analysis, Kaplan-Meier plots of DoR in the responding patients will be produced and appropriate descriptive summary statistics will be presented (n, number of responses that have progressed, median, quartile, minimum and maximum DoR).

Progression-free survival

PFS is defined as the time from randomisation (patients recruited under CSP version 7.0) or start of treatment (patients recruited prior to CSP version 7.0) until the date of objective disease progression or death (by any cause in the absence of progression) regardless of whether the patient withdraws from therapy or receives another anti-cancer therapy prior to progression. Patients who have not progressed or died at the time of analysis will be censored at the time of the latest date of assessment from their last evaluable RECIST assessment.

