However, if the patient progresses or dies after 2 or more missed visits, the patient will be censored at the time of the latest evaluable RECIST assessment. If the patient has no evaluable visits or does not have baseline data, they will be censored at Day 1 unless they die within 2 visits of baseline: in such a case, the death date will be used as the event date.

The PFS time will always be derived based on scan/assessment dates, not visit dates.

RECIST assessments/scans contributing towards a particular visit may be performed on different dates. The following rules will be applied:

- Date of progression will be determined based on the earliest of the dates of the component that triggered the progression.
- When censoring a patient for PFS, the patient will be censored at the latest of the dates contributing to a particular overall visit assessment.

Summaries of PFS (n, events, medians, quartiles, proportion progression free at **CCI** months and corresponding 95% CIs) and Kaplan-Meier plots will be provided by treatment group.

Progression-free survival based on investigator assessment will be analysed using a stratified log-rank test adjusting for the stratification used in randomisation for the generation of the p-value. The effect of treatment will be estimated by the HR together with its corresponding 95% CI for the CAS. An HR less than 1 will favour savolitinib plus osimertinib. The HR and its CI will be estimated from a Cox Proportional Hazards model (with ties = Efron and baseline stratification) and the CI calculated using a profile likelihood approach. If there are insufficient events per strata, a log-rank test will be used to analyse PFS instead of a stratified log-rank test.

Overall survival

OS is defined as the time from randomisation (patients recruited under CSP version 7.0) or the start of treatment (patients recruited prior to CSP version 7.0) until death due to any cause. Any patient not known to have died at the time of analysis will be censored based on the last recorded date on which the patient was known to be alive.

Note: Patients will be contacted for survival follow-up every 12 weeks. Patients should be contacted in the week after data cut-off for each analysis to establish survival status. The impact of cross over on OS may need to be assessed depending on the number of patients crossing over to savolitinib plus osimertinib. Further details will be provided in the SAP.

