
To determine the efficacy of savolitinib (300 mg od, 300 mg bid, and 600 mg od, respectively) in combination with osimertinib in patients with EGFRm+, MET-amplified/overexpressed (FISH10+ and/or IHC90+)^a, locally advanced or metastatic NSCLC who have progressed following treatment of ≥ 2L osimertinib.
	
 • ORR by investigator assessment in accordance with RECIST 1.1. • OS

To determine the efficacy of savolitinib (300 mg od, 300 mg bid, and 600 mg od, respectively) in combination with osimertinib in patients with EGFRm+, MET-amplified/overexpressed (FISH5+ and/or IHC50+)^b, locally advanced or metastatic NSCLC who have progressed following osimertinib.
	
 • ORR (except 300 mg od), DoR, and PFS by investigator assessment in accordance with RECIST 1.1 • OS

To determine the efficacy of (1) 300 mg od, 300 mg bid and 600 mg od of savolitinib in combination with osimertinib in patients with EGFRm+ MET-amplified/overexpressed (FISH 10+ and/or IHC90+)^{a,b}; (2) 300 mg od, 300 mg bid and 600 mg od of savolitinib in combination with osimertinib. in patients with EGFRm+ MET amplified/overexpressed (FISH5+ and/or IHC50+)^b; (3) savolitinib 300 mg bid in combination with osimertinib and savolitinib 300 mg bid in combination with placebo, respectively, in patients with EGFRm+ MET-amplified/overexpressed (FISH10+ and/or IHC90+)^a following treatment with 1L osimertinib.
	
 • ORR, DoR, and PFS assessed by BICR in accordance with RECIST 1.1.

To assess the impact of savolitinib and osimertinib on disease related symptoms and HRQoL in this patient population.	
 Mean change from baseline in EORTC QLQ-C30 and QLQ-LC13.
To evaluate the pharmacokinetics of osimertinib and savolitinib in this patient population.	
 Plasma concentrations of osimertinib, savolitinib and their metabolites.
To determine the prevalence of ctDNA clearance after osimertinib and savolitinib treatment in this patient population.	
 Total clearance in EGFR mutations at 6-weeks after therapy initiation (percentage and absolute change from baseline in EGFR mutation allele frequencies).
Safety Objectives:	Endpoints:

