6 CHANGES OF ANALYSIS FROM PROTOCOL

Although not specified in the current CSP version 7.0, Change in tumour size by investigator assessment in accordance with RECIST 1.1, best percentage change in TL tumour size, CNS ORR and CNS DoR by BICR assessments in accordance with RECIST 1.1 have been considered of interest for this study and will be explored.

Moreover, OS and PFS timepoints will be extended compared to CSP version 7.0 requirements.

DoR, PFS by investigator assessment in accordance with RECIST 1.1 will be assessed for CAS. Although present in CSP version 7.0 endpoints, DoR and PFS by ≥ 3 line of treatment will not be explored in this statistical analysis. Baseline assessments related to RECIST 1.1 will not follow CSP version 7.0 definition where 28 days window is required.

Finally, IUO grade status has been introduced. At this regard, ORR, DoR, PFS by investigator will be assessed in accordance with RECIST 1.1 using retrospective IUO grade MET testing on TPAS, SAF and CAS.

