8 APPENDICES

Appendix A Subgroup Analysis list

	ORR and PFS	
	TPAS	SAF*
Race		
Asian	X	X
Non-Asian		
Sex		
Male	X	X
Female		

Age group	X	X
<65 years		
>=65 years		
Line of treatment		
2nd line		X
>=3rd line		
Missing		
Prior platinum-based chemotherapy		
Yes		X
No		
Missing		
Prior platinum-based chemotherapy and line of treatment		
Yes and 2nd line		
Yes and >=3rd line		X
No and 2nd line		
No and >=3rd line		
Missing		
Immediately prior line of therapy		
Osimertinib		
Platinum-based chemotherapy		X
Other		
Missing		

Response to immediately prior line of therapy		
Yes and osimertinib		
Yes and platinum-based chemotherapy		
Yes and other		X
No and osimertinib		
No and platinum-based chemotherapy		
No and other		
Missing		
Immediately prior line osimertinib		
Osimertinib		
Not osimertinib		X
Missing		
Response to immediately prior line of therapy, osimertinib		
Yes and osimertinib		
Yes and not osimertinib		
No and osimertinib		X
No and not osimertinib		
Missing		
Number of previous EGFR TKI therapies		
1		
2		X
...		
Missing		
T790M status in baseline plasma	X	X
T790M+		
T790M-		

C797S mutation in baseline plasma		
C797S+	X	X
C797S-		
FISH+ allocation status		
Amplified (i.e., MET/CEP7 RATIO ≥ 2)	X	X
Polysomy (i.e., MET/CEP7 RATIO < 2)		
Missing		
IHC+ allocation status		
IHC90+		
IHC90 negative (FISH10+)	X	X
IHC50+		
IHC50 negative (FISH5+)		
IHC missing/unknown (FISH positive to enter study)		
FISH+ allocation status		
FISH 10+		
FISH 10 negative (IHC90+)	X	X
FISH 5+		
FISH 5 negative (IHC50+)		
FISH missing/unknown (IHC+ to enter study)		
Overall disease classification		
Metastatic	X	X
Locally advanced		
Missing		
EGFR mutation status [d]		
Exon 19 deletion	X	
L858R		

Known or treated brain metastases at study entry		X	
Yes (present at baseline or not present at baseline but with known or treated history)		X	
No (not present at baseline and not known or treated history of brain metastases)			
ECOG at baseline	0	X	
	1		
...			
Histological type		X	
Adenocacinoma			
Other			

* SAF : savolitinib 300 mg od + osimertinib (FISH10+ and/or IHC90+)

	OS		
	TPAS	SAF*	CAS
IHC+ allocation status			
IHC90+			
IHC90 negative (FISH10+)			
IHC50+	X	X	X
IHC50 negative (FISH5+)			
IHC missing/unknown (FISH positive to enter study)			
FISH+ allocation status			
FISH 10+			
FISH 10 negative (IHC90+)	X	X	X
FISH 5+			
FISH5 negative (IHC50+)			
FISH missing/unknown (IHC+ to enter study)			

* SAF : savolitinib 300 mg od + osimertinib (FISH10+ and/or IHC90+)

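### SAP 4.2.2.5 leaves out OS after at-least-2L osimertinib in FISH10+ and/or IHC90+ patients, a protocol secondary endpoint, and specifies no overall OS summary for the two randomised arms

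*SAP*

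**What the plan says.** **At-least-2L population.** Among the secondary objectives in Protocol 1.2 and Section 3 is efficacy of savolitinib 300 mg od, 300 mg bid and 600 mg od, each with osimertinib, in FISH10+ and/or IHC90+ "NSCLC who have progressed following treatment of ≥ 2L osimertinib". The endpoints are "ORR, DoR, and PFS, by investigator assessment in accordance with RECIST 1.1", with OS as a separate bullet.

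SAP Table 1 keeps the row ("locally advanced or metastatic NSCLC who have progressed following treatment of ≥ 2L osimertinib") with ORR and OS as endpoints. SAP Table 3, for the same objective, gives ORR only. SAP 4.2.2.5.2 has two SAF groups, neither of them this one. SAP Section 6 has a sentence beginning "Although present in CSP version 7.0 endpoints, DoR and PFS by" third or later line of treatment, which says these will not be explored. It does not mention dropping OS.

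**Randomised arms.** Protocol 9.4.3.2, the section that also defines OS, states: "Analyses for the efficacy secondary endpoints will be summarised using the TPAS, CAS, and SAF datasets". Under OS it adds "The impact of cross over on OS may need to be assessed depending on the number of patients" who cross over, and leaves the details to the SAP. SAP 3.2.1.1.6 repeats that the impact may need assessment but gives no method. SAP 4.2.2.5 opens with "OS will be summarised for TPAS set using the Kaplan-Meier methodology", continues with the SAF and stops. SAP Appendix A has a separate OS subgroup table, by IHC and FISH allocation status, with columns marked for the TPAS, the SAF and the CAS.

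**The concern.** If the analysis sections are programmed as written, a secondary endpoint listed in the protocol will not be reported, and the section meant to record departures from the protocol will not say so. A programmer cannot satisfy Table 1, Table 3 and 4.2.2.5.2 together.

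The CAS gap matters for a different reason. Patients on savolitinib plus placebo stop osimertinib at entry, and Protocol 2.3.1 and 4.2.1 name rapid progression through tumour flare as a risk of doing so. Every OS summary defined in 4.2.2.5 is for savolitinib plus osimertinib. The placebo arm therefore has no overall survival summary anywhere in the SAP, even though the protocol points to the CAS and to crossover when it discusses OS.

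**Working it through.** No sample size, power or event count is at issue, so there is no figure to reproduce. The check follows OS, population by population, through the documents.

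| Population with OS as an endpoint | Protocol 1.2 and Section 3 | SAP Table 1 | SAP Table 3 | SAP 4.2.2.5 |
|---|---|---|---|---|
| 300 mg bid, after 1L osimertinib, FISH10+/IHC90+ | OS | OS | OS (TPAS) | 4.2.2.5.1 |
| 300 mg od and 600 mg od, after 1L, FISH10+/IHC90+ | OS | OS | OS (SAF) | 4.2.2.5.2, first bullet |
| 300 mg od, 300 mg bid, 600 mg od, after at-least-2L, FISH10+/IHC90+ | OS | OS | ORR only | absent |
| 300 mg od, 300 mg bid, 600 mg od, FISH5+/IHC50+, any line | OS | OS | OS (SAF) | 4.2.2.5.2, second bullet |

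The protocol lists 4 OS populations and SAP 4.2.2.5 analyses 3, so 4 − 3 = 1 is missing. It covers three dose regimens.

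Does Section 6 cover the omission? SAP 4.2.2.2.2.1 defines line of treatment as the number of prior regimens plus 1, so two prior regimens give 2 + 1 = third line. The Section 6 sentence on third or later line is therefore best read as referring to this same objective. It names DoR and PFS. That matches Table 1, where DoR and PFS have gone from the row and OS has stayed. Read together, Table 1 and Section 6 say OS is kept; Table 3 and 4.2.2.5.2 say it is not.

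Does the any-line FISH5+/IHC50+ summary replace it? It may contain these patients, since SAP 4.1 says the two diagnostic populations overlap. But it pools lines of therapy and uses the lower MET cut-off, so it does not report the group the protocol asks for.

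For the randomised set, compare the endpoints as assessed by the investigator:

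| Endpoint | SAP section for the CAS |
|---|---|
| ORR | 4.2.2.2.1 |
| DoR | 4.2.2.3.3 |
| PFS | 4.2.2.4.3 |
| OS | none |

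Appendix A marks OS subgroups in 3 analysis sets (TPAS, SAF, CAS), while 4.2.2.5 defines a parent analysis in 2 (TPAS, SAF). The CAS subgroups thus have no overall analysis to sit under. The TPAS and both SAF groups in 4.2.2.5 are limited to savolitinib plus osimertinib, so the placebo arm is in none of them. Under Protocol 4.1.2 only placebo-arm patients can cross over, so the question about crossover and OS that the protocol leaves to the SAP arises in the CAS.

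**The case against.** The best counter-argument concerns the CAS. The randomised-comparison objective lists investigator ORR only, and the BICR objective adds ORR, DoR and PFS but not OS. In Protocol 9.4.3.2 the PFS text asks for summaries by treatment group and a hazard ratio in the CAS, whereas the OS text asks only for summaries and a Kaplan-Meier plot and names no arm. The crossover sentence is conditional. This stands: no listed endpoint is lost by omitting OS in the CAS, and the protocol does not require a hazard ratio or a test. What remains is the protocol's general statement naming the CAS, and an Appendix A column with no parent analysis. It is also true that 4.2.2.5 describes no OS subgroups for any set, so the mismatch with Appendix A is wider than the CAS.

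Harm to the placebo arm is also watched by other means: close monitoring in the first month, IDMC safety review of both arms, PFS by arm with a log-rank test and hazard ratio, adverse events with fatal outcome, and a listing of deaths. These lower the stakes. None of them gives time to death by arm. Crossover at progression, or after a futility declaration, will also blur any OS contrast. That argues for a descriptive output, not for none.

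Two stronger readings are tempting. A reader might infer that OS will not be shown by arm at all. SAP 4.1 presents analyses by assigned regimen, including 300 mg bid plus placebo, so the CAS subgroup outputs in Appendix A would presumably be split by arm; what is missing is the overall summary. A reader might also infer selective reporting of the at-least-2L endpoint. The documents do not support that: OS is still in Table 1, and the SAP amendment history openly records that Table 3 was revised for a reduced set of efficacy analyses and Section 4 aligned to it, though it does not name OS.

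**Conclusion.** The point holds on both parts, with different strength.

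The at-least-2L part is firm and rests on the text alone. One of four protocol OS populations, covering three dose regimens, is missing from Table 3 and 4.2.2.5.2, remains in Table 1, and is not declared as dropped in Section 6. It is an internal contradiction in the SAP and, if the analysis sections are followed, an undeclared change from the protocol.

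The CAS part is a gap in specification. It rests on the protocol's general statement about analysis sets, on the crossover question left to the SAP, and on Appendix A. It does not rest on the objectives table. The size is one missing output: an overall OS summary by randomised arm, which would be the only overall survival summary for the placebo arm.

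Both outputs are secondary and descriptive. Neither affects the primary ORR analyses. The one assumption made is that third or later line of treatment in Section 6 means the at-least-2L osimertinib objective; if it meant something else, the DoR and PFS omissions for that objective would be undeclared as well.

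**What to change.** 1. Add the at-least-2L FISH10+ and/or IHC90+ group (300 mg od, 300 mg bid, 600 mg od) to SAP 4.2.2.5.2, and add OS to the matching row of Table 3. If the sponsor has deliberately dropped it, remove OS from the Table 1 row instead and declare the change in Section 6.

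2. Add a CAS subsection to 4.2.2.5 with Kaplan-Meier OS by randomised arm, descriptive only, and the number and timing of crossovers. State that crossover dilutes the contrast. A hazard ratio is optional and descriptive; no formal test is needed.

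3. In that subsection, say how deaths after crossover are handled. SAP 2.2 keeps crossed-over patients under their initial allocation, while SAP 3.1.1 cuts off placebo-arm data at the start of the combination. A programmer could read the second rule as applying to OS.

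The cost is SAP wording and a few extra tables and figures. Survival status is already collected every 12 weeks and around each data cut-off (Protocol 8.1.3). The drawback is a by-arm OS comparison that is diluted by crossover and must be read with caution.
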